10.4 STATISTICAL ANALYSES

10.4.1 GENERAL APPROACH

RECIPE investigator [name] will oversee all data management and analysis for RECIPE DCC. The DCC is housed within the UAB School of Public Health. The DCC will ensure that the data collected and analyzed for this study are of the highest quality possible, and will be accomplished in part by having thorough edit checks as close to collection in time as possible, and updated as needed to guarantee high quality data through quality control and quality assurance. Edit checks will be reviewed by the statisticians, program manager, as well as other team members on an ongoing basis to evaluate whether any checks need to be added or any existing checks need to be modified. All data will be entered into the RECIPE electronic Data Entry System (eDES; Birmingham, AL) for seamless data management and auditing across the RECIPE sites (see MOOP Section 2.p). All analyses will be conducted using SAS (Cary, NC) Version 9.4 or higher or R-routines for specialty programs as needed.

One of the primary objectives of this feasibility pilot study is to determine if there is an overall reduction in immunogenicity leading to increased responders to pegloticase when MMF is co-administered in adults with chronic refractory gout. We have developed a decision table (see Figure 4) indicating when we will have sufficient evidence to move forward to a full scale clinical trial. Figure 4 compares the success rates in the peg+MMF arm (N=24) versus peg+PBO (N=8). The area in green is the area that we will lead us to recommend continuing to test the treatment approach in a full scale study assuming safety. This green area represents the area that achieves a significant (2 tailed p < 0.10) Fisher's exact test that peg+MMF is better than pegloticase alone. The yellow area represents an achievement of a 2-tailed p < 0.25. If the results end up in the yellow or red areas, we will examine the Ab assays to determine if there is a clear significant difference in immune response. Based on these sample sizes, the mean difference in Ab titer level needs to be at least 1 standard deviation unit apart to achieve 73% power. Nevertheless, this would be a large difference for a clinical outcome variable, but for a marker such as Ab titers this is not unreasonable. Should the titer distributions not be consistent with normality assumptions, nonparametric analyses using a Wilcoxon test will be used, since the titer levels are already measured on a log scale precluding a simple transformation to achieve normality. Participants before the 12 weeks primary endpoint that do not tolerate MMF, or are lost to follow-up, withdraw, or are otherwise not evaluable will be counted as failures but not non-responders in sensitivity analyses. MMF efficacy will be examined by the proportion of responders and tested against the control group rate using Fisher's exact test. Success rates of the efficacy primary outcome will be determined using summary statistics and 95% confidence intervals. In the event of missing antibody data, imputations will be considered to assure data completeness for our analyses using PROC MI and PROC MIANALYZE procedures with 5 replicates per value. All analyses will be conducted using SAS (V9.4, Cary, North Carolina).

Success without MMF Successes 2 3 4 5 6 7 Success with MMF 0.08 8 0.38 9 0.07 10 0.04 0.21 11 0.03 0.10 12 0.05 0.23 13 14 0.04 0.11 0.25 15 16 0.10 0.22 0.4 0.04 17 0.09 0.03 18 0.07 19 0.18 20 0.02 0.33 0.15 21 0.01 0.09 0.25 22 0.02 23 0.04 0.15 24 0.25

Figure 4. Decision to Pursue Future Clinical Trials (n = 32)

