4 OBJECTIVES AND ENDPOINTS

OBJECTIVES	ENDPOINTS	JUSTIFICATION FOR ENDPOINTS
Primary		
To assess efficacy of daily mycophenolate mofetil (MMF) to attenuate immunogenicity to pegloticase.	Proportion achieving and maintaining serum urate ≤ 6 mg/dL through 12 weeks, compared to concurrent controls.	Serum urate ≤ 6 mg/dL is slightly below the urate solubility threshold and this threshold has been the accepted standard for nearly all modern gout trials. 23-26 If the serum urate goal is not maintained before or at the 12 week mark, it will be assumed that the participant has developed clinically relevant anti-pegloticase antibodies and they will receive no further infusions. This assumption and subsequent discontinuation of pegloticase is consistent with the protocol of large phase III randomized controlled trials and the product label.
To assess the incidence and types of adverse events/infusion reactions potentially associated with a dual therapy regimen of pegloticase and MMF.	Incidence and Type of Adverse Events (AEs), Serious Adverse Events (SAEs), and Participant withdrawals due to AEs, anaphylaxis, and Infusion Reactions (IRs)	Safety profile is important because of the addition of an immune modulatory agent (MMF) that has potential of causing serious AEs
Secondary		
To assess durability of immune modulation after discontinuation	Absolute change in serum urate from baseline to wk 24; week 12 to 24 Proportion of participants with serum urate < 6 mg/dL through week 24; week 12 to 24	Assess if the efficacy of the short course of MMF continues following discontinuation.
To identify and characterize pegloticase immune response by immunoglobulin	Anti-pegloticase antibody isotypes (IgG/IgM), specificity, and titers	We anticipate that the primary Ab produced will be IgM anti-pegloticase but some participants, who will likely be the non-

OBJECTIVES	ENDPOINTS	JUSTIFICATION FOR ENDPOINTS
		responders will produce
		both IgM and IgG
		antibodies at earlier onset
To assess patient reported outcomes	PROs using PROMIS and Gout Impact score	To assess impact of the
(PRO)		intervention on patient
		reported outcomes
Tertiary/Exploratory		
Not applicable		

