8.2 PARTICIPANT DISCONTINUATION/WITHDRAWAL FROM THE STUDY

Participants are free to withdraw from participation in the study at any time upon request.

An investigator may discontinue or withdraw a participant from the study for the following reasons:

- Pregnancy
- Significant study intervention non-compliance
- If any clinical adverse event (AE), laboratory abnormality, or other medical condition or situation occurs such that continued participation in the study would not be in the best interest of the participant
- Disease progression which requires discontinuation of the study intervention
- If the participant meets an exclusion criterion (either newly developed or not previously recognized) that precludes further study participation
- Participant unable to receive study intervention for 1 infusion period

The reason for participant discontinuation or withdrawal from the study will be recorded on the Study Closeout/Withdrawl/Termination CRF. Participants who sign the informed consent form and are randomized but do not receive the study intervention may be replaced.

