8.3 LOST TO FOLLOW-UP

A participant will be considered lost to follow-up if he or she fails to return for 2 scheduled visits and is unable to be contacted by the study site staff.

The following actions will be taken if a participant fails to return to the clinic for a required study visit:

- The study coordinator will attempt to contact the participant and reschedule the missed visit within the 10 day window between pegloticase infusions and counsel the participant on the importance of maintaining the assigned visit schedule and ascertain if the participant wishes to and/or should continue in the study.
- Before a participant is deemed lost to follow-up, the investigator or designee will make every effort to regain
 contact with the participant. These contact attempts should be documented in the participant's medical record
 or study file.

- Should the participant continue to be unreachable, he or she will be considered to have withdrawn from the study with a primary reason of lost to follow-up.
- Based on our competitive enrollment of this study in the event a participant is lost to follow-up, withdraws
 consent and discontinues the study before the end of week 12 and is therefore unable to contribute to the
 primary outcome, the enrolling site will be afforded the opportunity to enroll a replacement participant.

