10.3 POPULATIONS FOR ANALYSES

The analysis population will include all enrolled participants who received at least 1 dose of study medication (mycophenolate mofetil or placebo) during treatment period (modified intention to treat, mITT). The protocol

population will be all participants who attend all study visits and complete the trial.

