10.4.2 ANALYSIS OF THE PRIMARY EFFICACY ENDPOINT(S)

MMF efficacy will be examined by the proportion of responders and tested against the control group rate using Fisher's exact test. Success rates of the efficacy primary outcome will be determined using summary statistics and 95% confidence intervals. As stated in section 10.4.1, should the success rates fall within the green area of **Figure 4** we will recommend testing in a larger study assuming safety and a demonstrated effect on Ab titers, our presumed intervening variable. We will examine failures and responders descriptively and via graphical methods.

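### The plan does not settle how dosed participants who leave, or do not tolerate MMF, before Week 12 enter the primary Fisher test; in borderline results one such participant can move the Figure 4 zone

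*Combined protocol and SAP*

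**What the plan says.** - **Population (10.3).** "The analysis population will include all enrolled participants who received at least 1 dose of study medication", that is, MMF or placebo. This is the mITT set.
- **Endpoint (section 4).** "Proportion achieving and maintaining serum urate" at or below 6 mg/dL through 12 weeks, compared with controls.
- **Primary test (10.4.2).** "MMF efficacy will be examined by the proportion of responders and tested against the control group rate" by Fisher's exact test. The section does not define the denominator. It adds: "We will examine failures and responders descriptively and via graphical methods".
- **Leavers and intolerance (10.4.1).** Participants who before Week 12 do not tolerate MMF, are lost, withdraw or are otherwise not evaluable "will be counted as failures but not non-responders in sensitivity analyses".
- **Replacement (8.3).** A participant who is lost, withdraws consent and "discontinues the study before the end of week 12 and is therefore unable to contribute" to the primary outcome may be replaced: "the enrolling site will be afforded the opportunity to enroll a replacement participant". This is not limited to people never dosed. Section 8.2 mentions replacement only for those "randomized but do not receive the study intervention may be replaced", which fits mITT.
- **Non-responder (8.1).** Two consecutive serum urate (sUA) values above 6 mg/dL.
- **Missing data (10.4.7).** Missing outcomes may be imputed where this is judged appropriate; the primary outcome is not exempted.
- **Decision (10.4.1, 10.4.2, Figure 4).** Green is two-tailed Fisher p<0.10 favouring MMF, and yellow is p<0.25, at 24 v 8. Green supports a full-scale trial, given safety and an antibody-titer effect. Yellow or red sends the team to the antibody assays.

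**The concern.** The primary outcome has two categories, so every dosed participant must be a success, a failure, or outside the table. The plan gives no single answer for someone who leaves before Week 12 without a recorded urate failure. Section 10.3 keeps that person. Section 10.4.1 makes that person a failure, but only for sensitivity analyses. Section 8.3 says the person cannot contribute and may be replaced. Followed literally, 8.3 and the 10.4.1 wording would drop or replace dosed participants after randomisation in the test behind the green zone.

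MMF intolerance is a separate mismatch. Under 7.1.1 an intolerant participant may continue on a lower dose and have complete urate data. Section 10.4.1 counts that person as a failure whatever the urate; the section 4 endpoint goes by urate alone.

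At stake is the numerator and denominator of the Figure 4 comparison. With eight controls, one reclassified participant can matter. If the rule is chosen after unblinding, it can be chosen knowing which zone it produces.

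**Working it through.** **Inputs.** Arms of 24 and 8; green p<0.10 and yellow p<0.25, two-sided (10.4.1). Success rates of 60% control and 80% MMF (10.2). The documents give no exit rate, so the exit rates below are assumptions.

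**Plan's own figures.** Two-sided Fisher at 24 v 8 gives, for placebo 5/8: 20/24 p=0.33, 21/24 p=0.15, 22/24 p=0.09. For placebo 6/8, 22/24 gives p=0.25. These values appear in Figure 4, so its denominators are 24 and 8.

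**Single results.** In the MMF rows one non-success in the MMF arm is a leaver; in the last row it is a placebo leaver.

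| Case | As failure | Excluded | Replaced by a responder |
|---|---|---|---|
| Placebo 4/8, MMF leaver | 20/24, p=0.152 | 20/23, p=0.053 | 21/24, p=0.047 |
| Placebo 5/8, MMF leaver | 21/24, p=0.148 | 21/23, p=0.093 | 22/24, p=0.085 |
| MMF 22/24, placebo leaver | v 5/8, p=0.085 | v 5/7, p=0.212 | not computed |

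In the two MMF rows, the last column is also the result if an MMF-intolerant participant with urate at or below 6 mg/dL is counted as a success instead of a failure. If the original stays as a failure and a responding replacement is added, the p-values are 0.074 (21/25 v 4/8) and 0.137 (22/25 v 5/8).

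**How common such cells are.** Take placebo 3 to 6 of 8 and MMF 15 to 23 of 24: 4 x 9 = 36 cells. Excluding one MMF leaver changes the zone in 7, and 4 of those become green. Nearest the planned rates, 19/24 v 5/8 gives p=0.378. Excluding one, two, three and four leavers gives 0.335, 0.300, 0.112 and 0.058, so green needs four exclusions.

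**Chance of green.** P(green) is the sum of the binomial probabilities of all tables with p<0.10 and a higher MMF rate. Assume 20% exits on MMF and none on placebo.
- As failures: n = 24 and 8, MMF success = stayer rate x 0.80.
- Excluded: evaluable MMF n is binomial (24, 0.80).
- Replaced: n = 24 and 8 at stayer rates.

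| Scenario | MMF stayer rate | MMF rate as failures | As failures | Excluded | Replaced |
|---|---|---|---|---|---|
| (a) all leavers true failures, 60% v 60% overall | 0.60/0.80 = 0.75 | 0.60 | 3.3% | 15.2% | 15.8% |
| (b) leaving unrelated, stayers 60% v 60% | 0.60 | 0.48 | 0.6% | 3.7% | 3.3% |
| (c) leaving unrelated, stayers 80% v 60% | 0.80 | 0.64 | 5.3% | 22.7% | 24.3% |

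Under the assumption in (a), equal exits of 10% or 20% in both arms give 3.5-3.6% with exclusion or replacement, so almost no distortion. Exits of 10% on placebo only give 1.7% excluded and 1.5% replaced, which works against MMF.

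**The case against.** A reader might infer that the plan excludes leavers from the primary analysis. It does not say so. The single mITT set, the endpoint wording, the word failures, the pairing of failures with responders in 10.4.2 and the fixed 24 and 8 all lean towards the full denominator. Section 8.3 can be read as an enrolment provision only. Against the 8.1 definition, the odd phrase in 10.4.1 also makes sense: it separates leavers from urate-defined non-responders. All of this stands, and it makes exclusion or replacement one permitted reading, not the stated rule. It does not close the gap, because the only failure rule for leavers is tied to sensitivity analyses and 8.3 is silent on the replaced original.

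The affected group is also smaller than all early exits. Someone with two consecutive high urates already has a documented outcome under every reading. Scenario (a) therefore needs 20% of the MMF arm to leave as true failures with none yet recorded, and no passage supports that. MMF intolerance without loss or withdrawal is not covered by 8.3 at all; there the problem is classification, not replacement.

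Finally, section 10.4.3 calls the analyses descriptive, and antibody evidence is consulted in every zone. That limits the consequence but does not remove it: a pre-specified decision table still needs a defined denominator.

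**Conclusion.** The concern holds as an unreconciled rule in the current text: 10.3 keeps dosed leavers, while 10.4.1 and 8.3 permit a primary test without them. The consequence is confined to borderline results, where one participant can change the zone in either direction; most cells do not change.

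The direction of any bias depends on two unknowns: which arm loses more participants, and whether leaving is related to response. A reader might take 15-16% as the false-green rate of this design. The documents do not support that, because it rests on assumed 20% MMF-only exits that are all true failures. If leaving is unrelated to response, exclusion or replacement stays near the 3.3% no-exit value, and counting leavers as failures is the conservative choice (0.6%).

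Nor is a zone change a go/no-go change. Green also needs safety and a titer effect, and yellow or red leads to the antibody assays. This should be fixed, but it does not invalidate the design.

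**What to change.** 1. **10.4.2.** State that the primary Fisher test uses all mITT participants, and that anyone without documented sUA at or below 6 mg/dL maintained through Week 12, including those lost or withdrawn, counts as not achieving the endpoint. Make evaluable-only and imputed analyses sensitivity analyses, and reword 10.4.1 to match.
2. **8.3.** State that dosed originals stay in the primary analysis and that replacements are additional. Compute Fisher's p on the actual Ns when they differ from 24 and 8, since Figure 4 cannot then be read directly.
3. **MMF intolerance.** Reconcile 10.4.1 with the section 4 endpoint for a participant whose urate stays at or below 6 mg/dL. Fix one classification before unblinding and report the other as a sensitivity analysis.

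The change is wording only: no new participants, visits or tests. It has a real price. If exits are more frequent on MMF and unrelated to response, the chance of green falls, as in scenario (c): from 24.3% replaced or 22.7% excluded to 5.3% as failures. The evaluable-only sensitivity analysis would show that case.

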10.4.2 ANALYSIS OF THE PRIMARY EFFICACY ENDPOINT(S)

MMF efficacy will be examined by the proportion of responders and tested against the control group rate using Fisher's exact test. Success rates of the efficacy primary outcome will be determined using summary statistics and 95% confidence intervals. As stated in section 10.4.1, should the success rates fall within the green area of **Figure 4** we will recommend testing in a larger study assuming safety and a demonstrated effect on Ab titers, our presumed intervening variable. We will examine failures and responders descriptively and via graphical methods.

10.4.3 ANALYSIS OF THE PRIMARY SAFETY AND SECONDARY ENDPOINT(S)

The *primary safety aim* will examine the number of patients experiencing the event and the total number of events, their severity and relatedness to study drug will be summarized and all AEs and SAEs reported. Ascertaining safety outcomes will be mostly descriptive and the confidence intervals will remain wide for the proportion of responders, based on n = 32, but strong evidence to proceed with a larger trial is necessary.

The *secondary aims* are to: 1) Determine the 6 month durability of immune modulation after discontinuation of the short course of MMF by: a) assessing the absolute change in serum urate from baseline to Week 24, and Week 12 to Week 24, and b) determining the proportion of participants with serum urate ≤ 6 mg/dL through 24 weeks, and Week 12 to Week 24; 2) Identify and characterize the pegloticase immune response by immunoglobulin isotypes (IgG and IgM), specificities, and antibody titer, and 3) Examine patient reported outcomes (PROs) using the NIH supported Patient Reported Outcomes Measurement Information System (PROMIS)^{57,58} and Gout Impact Scale (GIS)^{59,60} instruments. For safety we will assess the incidence and types of adverse events / infusion reactions. The number of patients experiencing the event and the total number of events, their severity and relatedness to study drug will be summarized and all AEs and SAEs reported. Secondary endpoints including AEs across groups will be summarized using frequency and percentages. Continuous secondary outcome variables will be summarized using means with standard deviation (SD), and/or median and interquartile ranges (IQR) with 95% confidence intervals and compared by groups using t-tests or Wilcoxon tests as appropriate. Pegloticase Ab titers will be qualitatively analyzed for possible relationships with sUA lowering and the risk of IRs. Six month durability of response to MMF will be explored to assess if there is a threshold

^{*} Dash indicates a highly significant 2 tailed p-value using Fishers exact test

effect or pattern of response with anti-pegloticase Ab titers/types. This aim will be supported by analyses that compares the treatment groups using two group t-tests and regression analyses that include the time of the sampling (an offset) to adjust for any 12 or 24 week samples that may be taken earlier at the time of failure or dropout. Repeated measures assessments using all Ab data (both data points: baseline and last observation) will be assessed using random effects in PROC MIXED to assess the variability in response over time. Comparisons will be assessed using pre-specified contrasts. Analyses of the sUA will be similarly assessed using PROC MIXED with random effects for participant. In addition, addressing the secondary aim: b) determining the proportion of participants with sUA ≤ 6 mg/dL through 24 weeks, and Week 12 to Week 24; will be examined using Fisher's exact test. Continuous models estimating the areas under the dose-time curve with estimation based on using the trapezoidal rule will be constructed and adjusted for time under study yielding an average sUA during the observation period. These areas under the curve will be compared using similar linear models with an offset for the time under study. Exploratory analyses will assess association of covariates within group areas under the curve; 2) Identify and characterize the pegloticase immune response by immunoglobulin isotypes (IgG and IgM), specificities, and Ab titer.

These secondary outcome variables will be summarized using means with standard deviation, confidence intervals, and/or median and interquartile ranges, dependent on their distribution and plots of their response alone and in combination. Secondary endpoints will examine different definitions of sUA levels by plotting the initial values versus change values on the unbiased outcome results and time weighted averages; and 3) Examine PROs using the NIH supported Patient Reported Outcomes Measurement Information System (PROMIS)^{57,58} and Gout Impact Scale (GIS)^{59,60} instruments; these will use similar approaches of descriptive statistics, plots of PROs versus outcomes and correlations. The PROs will be summarized by change over time using means, 95% confidence intervals and compared between responder and non-responder status. We do not plan to control for the repeated testing using adjustments for multiple comparisons since this is a feasibility trial and since statistical significance is not the goal as it would be in a pivotal trial. The sample size is small and we see these secondary as well as primary analyses as descriptive. The p-values will be calculated, but will take the totality of the evidence into account in the interpretation. We considered using hierarchical testing such that each test would be done at the 0.05 level, but the low power argues that such could easily lead back to not considering secondary endpoints.

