5 STUDY DESIGN

5.1 OVERALL DESIGN

Hypothesis: MMF for 12 weeks can safely attenuate immunogenicity conferred by pegloticase as determined by the proportion of participants achieving and maintaining an sUA ≤ to 6 mg/dL through 12 weeks, compared to concurrent controls

Phase of trial: Phase II

Design of trial: Randomized, double-blind, placebo controlled

Single or multi-site: Multisite (UAB, University of Michigan[UM], and up to 6 to be named sites)

Number of Arms: Two arms; Intervention Arm: pegloticase + MMF (peg + MMF); Placebo Comparator Arm: pegloticase

+ placebo (peg + PBO)

Methods to minimize bias: Participants will be randomized 3:1 to either peg+MMF or to peg+PBO. Randomization allocation will be balanced by site to achieve 24 peg+MMF and 8 peg+PBO using the double-blind design

During the first 12 weeks, participants randomized to the peg+MMF arm will receive a combination of pegloticase and MMF. Patients experience reduced immunogenicity when a loading dose of anti-proliferative agent is administered *prior* to a monoclonal antibody in other disease states, ²⁷⁻³⁰ thus, for those randomized to the peg+MMF arm we will begin a MMF run-in at 500 mg/twice per day for the first week, and if tolerated titrate the dose up to 1000mg/twice per day for the second week of run-in prior to initial pegloticase infusion. MMF (or matching PBO in the other arm) will be titrated to 1000 mg/twice per day (a standard, well-tolerated dose used in other rheumatic diseases)⁶ concurrent with the first pegloticase infusion. Next, a total of up to 12 infusions of pegloticase 8 mg IV will be administered on a biweekly basis. To understand the long-term efficacy (durability) and safety of this approach, and to minimize the exposure to MMF, following the first 12 weeks of dual therapy phase, all participants will be given an additional three months of open-label pegloticase only therapy (see **Figure 1**) and will be followed.

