5.3 JUSTIFICATION FOR DOSE

For those randomized to the peg+MMF arm we will begin a MMF run-in at 500 mg/twice per day for the first week, and if tolerated titrate the dose up to 1000mg/twice per day for the second week of run-in prior to initial pegloticase infusion. MMF (or matching PBO in the other arm) will be titrated to 1000 mg/twice per day, the standard, well-tolerated dose used in other rheumatic diseases⁶ (concurrent with the first pegloticase infusion).

All participants in the study will receive pegloticase at the FDA approved dose of 8 mg administered intravenously every 2 weeks for a total of 6 infusions over a 12-week treatment period, and over an additional 12-week pegloticase opt-in follow-up period (per standard of care).

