7.3 MEASURES TO MINIMIZE BIAS: RANDOMIZATION AND BLINDING

Participants will be randomized 3:1 to either pegloticase + MMF (Peg+MMF) or to pegloticase + placebo (peg+PBO). Randomization allocation will be balanced in time and by site to achieve 24 peg+MMF and 8 peg+PBO using a double-blind design. Treatment assignment will be determined by a random number generator and stratified by site using a central randomization system to ensure the 24/8 allocation. If any concerns arise during the randomization procedures, both the pharmacist and study coordinator will contact the Data Coordinating Center (DCC) at UAB. The UAB IDS will be responsible for assignment of randomization sequence. A drug log will be used to track the study drug from pharmacy to each randomized study participant. The centralized management of the medication will allow maintenance of a double-blind trial.

As all participants and study investigators will be blinded to treatment assignment. If there is a serious adverse event, then unblinding will be discussed and if deemed necessary to unblind the participant, then the ID of the unblinded participant, reasons for unblinding, name of the pharmacist and a list of whomever becomes unblinded will be kept in the study binder and centrally at the Data Coordinating Center and Central Pharmacy. The pharmacist will contact that participant's primary physician about the exposure. If necessary, the participant will be withdrawn from the study. NIAMS and the DSMB via KAI will be informed of any unexpected unblinding via email or at the scheduled DSMB meetings.

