10.2 SAMPLE SIZE DETERMINATION

As a pilot proof of concept study, we are not able to fully power the trial to detect a difference between a rate of 60% success vs the success rate after induction by MMF, which we hypothesize will be 80% or more. If we powered the study with 80% power, 2 sided type I error of 5%, we would require 82 participants per group to demonstrate this difference with a treatment and control group. To ensure resources are not wasted, we will confirm that a future larger study is worth pursuing based on results of this pilot study. We have included a decision table based on Fisher's exact tests to define how results will inform our decision about a future full scale study (see section 10.4.1).

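### The Week 12 to Week 24 durability comparison has no stated denominator or rule for earlier failures, so on available data it compares only Week 12 survivors, a group selected by treatment.

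*Combined protocol and SAP*

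**What the plan says.** Durability after stopping MMF is the first secondary objective (Section 4). Section 10.4.3 describes it by the change in serum urate (sUA) from baseline to Week 24 and from Week 12 to Week 24, and by "determining the proportion of participants with serum urate ≤ 6 mg/dL through 24 weeks, and Week 12 to Week 24". The same section says that the proportion "through 24 weeks, and Week 12 to Week 24; will be examined using" Fisher's exact test. Continuous secondary outcomes are compared between groups by t-test or Wilcoxon test, with mixed models for sUA.

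These rules decide who has Week 12 to 24 data:

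- **Stopping pegloticase.** Section 4 gives no further infusions to patients who do not maintain the sUA goal before or at Week 12. Section 8.1 discontinues patients after two consecutive values above 6 mg/dL.
- **Visits after stopping.** Section 8.1 and the reminder under Visit 17 in Section 9 send these patients to Visit 17, which Section 8.1 places two weeks after stopping, and then to Visits 18 to 20. Table 1 schedules no sUA at Visits 18 to 20.
- **A conflicting statement.** The Follow-up paragraph that closes the visit descriptions in Section 9 promises follow-up for the full study period with all data collected on schedule.
- **Population.** Section 10.3 defines mITT as everyone enrolled who took at least one dose of MMF or placebo.
- **Continuation.** Section 5.1 says "all participants will be given an additional three months of open-label pegloticase only therapy". Section 5.3 describes treatment "over an additional 12-week pegloticase opt-in follow-up period", and Section 7.2.2 does the same.

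**The concern.** Response at Week 12 is a post-randomisation outcome, and raising it is the purpose of MMF. If only patients still responding at Week 12 have Week 12 to 24 urate, the two arms in that comparison are no longer the randomised groups. The MMF survivors include patients who responded only because of MMF. The placebo survivors have no such patients.

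Nothing in the plan repairs this. The offset in Section 10.4.3 adjusts for samples taken early, not for who is left. The failure rule in Section 10.4.1 concerns patients not evaluable before the 12-week endpoint, and only in sensitivity analyses. The imputation in Section 10.4.7 draws on visits that flank a missed one, and early failures have no later visit with sUA.

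What is at stake is the reading of durability, which Section 9 calls essential for future studies. The plan could report two durability results with opposite signs and does not say which one governs.

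**Working it through.** **1. Who has Week 12 to 24 data.** With Visit 17 two weeks after stopping, a patient who fails before about Week 10 has that visit before Week 12. This patient has no Week 12 value and no scheduled value from Week 14 to Week 24, so the Week 12 to 24 change cannot be computed. The proportion is affected in the same way if it is computed on available data.

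**2. Inputs from the plan.** Section 10.2 takes "a rate of 60% success" for control and an MMF rate "which we hypothesize will be 80% or more". Section 7.3 has randomisation "stratified by site using a central randomization system to ensure the 24/8 allocation".

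**3. The plan's own figure.** Section 10.2 states "80% power, 2 sided type I error of 5%, we would require 82 participants per group". A pooled-variance two-proportion formula without continuity correction, at 60% against 80%, gives 82 per group. The figure reproduces, so these rates are the plan's working values. The plan gives no figure for the Week 12 to 24 endpoints.

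**4. Expected Week 12 responders.**
- MMF: 24 × 0.80 = 19.2
- Placebo: 8 × 0.60 = 4.8

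**5. Model (assumptions, not in the documents).** MMF only adds responders: 60% respond in either arm and a further 20% respond only with MMF. Let dA be the probability of staying in response to Week 24 for those who respond anyway, and dI the same for those who respond only with MMF. The share of MMF survivors without a placebo counterpart is 0.20 / 0.80 = 25%.

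**6. Formulas.**
- Week 12 responders only: MMF = (0.6·dA + 0.2·dI) / 0.8 and placebo = dA. Difference = 0.75·dA + 0.25·dI − dA = 0.25·(dI − dA).
- All mITT patients, with early failures counted as failures: MMF = 0.6·dA + 0.2·dI and placebo = 0.6·dA. Difference = 0.2·dI.

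**7. Results.**

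| dA | dI | Responders only: MMF vs placebo | Difference (points) | mITT: MMF vs placebo | Difference (points) |
|---|---|---|---|---|---|
| 0.80 | 1.00 | 85% vs 80% | +5 | 68% vs 48% | +20 |
| 0.90 | 0.90 | 90% vs 90% | 0 | 72% vs 54% | +18 |
| 0.90 | 0.50 | 80% vs 90% | −10 | 64% vs 54% | +10 |
| 0.90 | 0.25 | 74% vs 90% | −16 | 59% vs 54% | +5 |
| 1.00 | 0 | 75% vs 100% | −25 | 60% vs 60% | 0 |

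Over dA from 0.80 to 1.00 and dI from 0 to 1.00, the responder-only difference runs from −25 to +5 points and the mITT difference from 0 to +20.

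**8. At the actual sample size.** In 200,000 simulated trials of 24 and 8 patients with dA = 0.90 and dI = 0.50, the responder-only estimate was below zero in 74% and the mITT estimate in 28%. With dA = dI = 0.90 the figures were 56% and 16%; the mean responder-only difference was then zero.

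**9. One integer example.** Suppose 19 of 24 and 5 of 8 respond at Week 12, and 16 and 5 still respond at Week 24. Among Week 12 responders this is 16/19 = 84% against 5/5 = 100% (Fisher p = 1.00). On the mITT denominator it is 16/24 = 67% against 5/8 = 62.5%.

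**The case against.** A reader might infer that the plan restricts the Week 12 to 24 analysis to Week 12 responders. It does not say so. Section 10.3 states an mITT population, Section 8.1 says that stopping treatment is not leaving the study, and the Follow-up paragraph in Section 9 promises full data collection. This stands as far as the wording goes: for the proportion, the restriction is only the likely result of computing it on available data. It does not rescue the change score, which needs values that the discontinuation schedule does not provide.

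A reader might also infer that the comparison is necessarily biased against MMF. The documents do not support that. The responder-only difference is negative only if dI is below dA. It is zero when they are equal and positive when dI is higher, and the documents give neither rate. At dI = 0 the mITT benefit is also zero, so that end of the range is not an effective course made to look harmful.

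The opt-in wording could be read as a second round of selection. It is only a mismatch with the statements that all participants continue; nothing shows that patients will choose.

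Finally, the through-Week-24 proportion in the same sentence already allows a randomised comparison, Section 10.4.3 calls these analyses descriptive, and the decision on a larger trial rests on the 12-week table, antibodies and safety (Sections 10.4.1 and 10.4.2). This limits the impact. It does not remove the point, because the plan still calculates p-values and names a between-arm test for the Week 12 to 24 proportion.

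**Conclusion.** The point holds as a gap in definition. The Week 12 to 24 endpoints have no stated denominator and no rule for patients who fail before Week 12. Following the discontinuation schedule makes the change score a non-randomised contrast among survivors, and probably the proportion too. At the planned response rates that contrast involves about 19 and 5 patients.

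Its size depends on assumptions outside the documents: that MMF only adds responders, and the ranges chosen for dA and dI. Within them, the responder-only result can have the opposite sign to the mITT result when MMF-dependent responders relapse more, and it shows no benefit when they relapse equally. The consequence is a possible misreading of the first secondary objective. It does not affect the primary endpoint or the decision table.

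**What to change.** - Make the proportion with sUA ≤ 6 mg/dL through Week 24, on the full mITT denominator, the single tested between-arm durability comparison. Count loss of response or stopping at any time as not durable.
- Report the Week 12 to 24 proportion and sUA change among Week 12 responders, by arm, with intervals and no between-arm p-value. State the denominator in each arm.
- Do not place the Week 12 to 24 proportion on the mITT denominator as well. With early failures counted as failures it becomes the same endpoint as the through-Week-24 proportion.
- Reconcile the visit schedule after stopping (Section 8.1 and the Visit 17 reminder in Section 9) with the promise of full scheduled data collection (Follow-up paragraph in Section 9).
- Reconcile the opt-in wording in Sections 5.3 and 7.2.2 with Sections 5.1 and 7.1.1, where participants continue.

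The cost is wording in the analysis section and the protocol, and the loss of between-arm testing for Week 12 to 24. The statistical change needs no extra patients or visits.
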